#### **4.1 Randomisation and Blinding**

Patients who fit the inclusion and exclusion criteria would be recruited into the study. We will perform a 1:1, block-of-4 randomisation using a computer-generated programme performed by an independent research administrator who is not part of the surgical team.

They will be allocated only after they are examined under anaesthesia. Allocation is provided in a concealed opaque enveloped that is provided by the research administrator on the day of the operation. Thus, the patient is blinded to the procedure. There will also be no cross-over from one study arm to another.

An independent research administrator, not part of the randomisation process, will also contact the patient 3 months and 1 year after the procedure as mentioned above.

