## **4 STUDY DESIGN**

This is a single-center, double-blind randomized controlled trial to be conducted in Sengkang General Hospital.

All patients presenting to the clinic or admitted for symptomatic haemorrhoids would be assessed for recruitment.

Figure 1 shows the enrolment process of the study population in the trial. Patients will be seen in the

clinic or in the wards for symptomatic haemorrhoids. All these patients would be approached and be introduced to this study but not recruited yet.

Patients older than 40 years-old with no recent colonoscopy (within 5 years) would need to have a colonoscopic evaluation of the colon after the index admission/clinic visit.

Those younger than 40 would be advised to have a rigid sigmoidoscopy on the day of the operation during the examination under anaesthesia. Only after agreement to the above, the patient would be recruited into the study. They would then be educated on the peri-operative questionnaire separately by a research administrator after recruitment into the trial.

The peri-operative package is split into pre- and post-operative components and will include basic demographics, baseline haemorrhoid-specific QoL questionnaires, VAS scales for POD0-10 and details of the intraoperative procedure and intraoperative description of the haemorrhoids.

Patients who fit the inclusion and exclusion criteria would be recruited into the study. We will perform a 1:1, block-of-4 randomization using a computer-generated programme performed by an independent research administrator who is not part of the surgical team.

They will be allocated only after they are examined under anaesthesia. Allocation is provided in a concealed opaque envelope that is provided by the research administrator on the day of the operation. Thus, the patient is blinded to the procedure. There will also be no cross-over from one study arm to another.

Potential Difficulties and Alternative Approaches to achieve the aims:

Difficulty of recruitment of patients into the trial may be potentially present especially for a procedure that is new in Singapore. Patient counselling and explanation of the procedure would be important and offering a short video clip of the procedure may be helpful. The procedurists/co-investigators of the study team would also be trained by a regional practitioner of the technique before the initiation of the trial to ensure proficiency for reassurance.

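### A fixed block size of 4, printed in the protocol of a single-centre trial, lets anyone who tracks the whole list deduce up to one third of allocations before the envelope is opened

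*Protocol*

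**What the plan says.** Section 4.1 sets out the method as 1:1, "block-of-4 randomisation using a computer-generated programme", run by an independent administrator outside the surgical team. Section 4 gives the same 1:1 ratio and block size. Neither section mentions a second block size or a stratification factor.

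On timing, section 4.1 states: "They will be allocated only after they are examined under anaesthesia". On concealment: "Allocation is provided in a concealed opaque enveloped that is provided by the research administrator on the day of the operation". The protocol does not say who opens the envelope.

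Section 4 opens with "This is a single-center, double-blind randomized controlled trial", but the only person described as blinded is the patient: "Thus, the patient is blinded to the procedure". Under section 6.5 that blinding ends at the 4-6 week clinic review. The operating surgeon cannot be blinded to the procedure being performed.

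There is more than one operator: "The procedurists/co-investigators of the study team would also be trained by a regional practitioner of the technique". The number is not given.

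**The concern.** Opaque envelopes protect allocation only while the next allocation cannot be worked out from the earlier ones. With short blocks of one fixed size, a reader who knows that size and keeps count can sometimes work it out. Here the size is printed in a document that the co-investigators read, and the list appears to be a single one for a single hospital.

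The timing adds to the concern. Allocation comes after the examination under anaesthesia, when the surgical team has just assessed the disease. Someone who could predict the next arm at that point could, in principle, let the prediction influence whether a particular patient goes on to allocation. If the patients kept or left out differed in ways that affect post-operative pain, the arms would no longer be comparable on the primary outcome, the daily VAS over the first 10 days (section 2.2).

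**Working it through.** The protocol gives no figure for predictability. Its only related number is the sample size, which fixes the length of the list, so that is checked first.

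**Length of the list (section 9.1).** Inputs: 50% against 25%, power 80%, alpha 5% (taken as two-sided), 10% loss.
- n per arm = [1.96 × √(2 × 0.375 × 0.625) + 0.8416 × √(0.25 + 0.1875)]² / 0.25² = (1.342 + 0.557)² / 0.0625 ≈ 57.7, so 58.
- 58 × 1.1 = 63.8, so 64 per arm and 128 in total. The protocol's figure is reproduced.
- 128 / 4 = 32 blocks.

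**Certain allocations, one observer who knows all earlier allocations and the block boundaries.** A block of 4 has six equally likely balanced orders.
- Positions 1 and 2 are never forced.
- Position 3 is forced when the first two are alike: probability 1/3.
- Position 4 is always forced.
- Share = (0 + 0 + 1/3 + 1) / 4 = 1/3. Over 32 blocks, 32 × 4/3 = 42.7, about 43 of 128.

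**Best-guess accuracy, same observer.** The chances of a correct guess by position are 1/2, 2/3, 2/3 and 1. The mean is 2.833 / 4 = 70.8%, against 50% by chance.

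**Certain allocations, k surgeons who know only their own cases.** Assume that cases are split equally at random, nothing is shared, and each surgeon knows the position in the block.
- At position 3 the surgeon must have done both earlier cases and they must be alike: 1/k² × 1/3.
- At position 4, two of the three earlier cases share an arm, and the surgeon must have done both: 1/k².
- Share = (1/(3k²) + 1/k²) / 4 = 1/(3k²).
- k = 2: 1/12 = 8.3%, about 11 of 128. k = 3: 1/27 = 3.7%, about 5. k = 4: 1/48 = 2.1%, about 3.
- Simulation gives 8.3%, 3.7% and 2.1%.
- A surgeon who did not know the block position could deduce fewer still.

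**Alternatives, observer with full knowledge.** Fixed sizes are enumerated exactly. Mixed sizes come from 1,500 simulated 128-patient lists with sizes equally likely, and the observer also knows the set of sizes.

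| Block scheme | Certain | Best guess correct |
|---|---|---|
| Fixed 4 (protocol) | 33.3% | 70.8% |
| Fixed 6 | 25.0% | 68.3% |
| Fixed 8 | 20.0% | 66.6% |
| Random 4, 6 | 5.5% | 69.2% |
| Random 4, 6, 8 | 2.3% | 68.0% |

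**Which end of the 2% to 33% range is realistic.** The protocol does not settle this, but it describes routes by which knowledge could be pooled. Sections 8.2 and 12.2 give co-investigators access rights for data entry and analysis, through the PI. Section 4 includes details of the procedure among the data collected. Section 7.4 has every complication reviewed by the whole study team. None of these amounts to a running tally of allocations, and none rules one out.

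**The case against.** The strongest reply has four parts.

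- **Partial knowledge.** Each surgeon performs only some of the operations, so nobody need know the whole list. This stands: one third is an upper bound.
- **Control of the envelope.** A reader might infer that the surgeon decides whether the envelope is opened. The documents do not support that. The list is generated by someone outside the surgical team, and a research administrator provides the envelope. The protocol is silent on who opens it, and silence is not evidence of surgeon control.
- **Narrow opportunity.** Patients have been assessed, consented and recruited before theatre (sections 3.2, 4 and 12.1). No exclusion criterion in section 3.4 rests on severity seen under anaesthesia, and leaving an anaesthetised participant unallocated would be conspicuous. Reordering the theatre list is possible, but it happens before the examination and so cannot use its findings. This largely stands. What remains is that section 4 advises patients under 40 to have rigid sigmoidoscopy during that same examination, so an eligibility question can arise just before allocation, and the protocol sets no rule for exclusion at that point.
- **Limited gain.** Varying the block size lowers best-guess accuracy by only about 3 percentage points. This is true. The benefit lies in removing certainty.

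**Conclusion.** The point holds as a weakness in a stated design choice. A fixed, disclosed block of 4 at one centre, with operators who cannot be blinded, allows up to one third of allocations (about 43 of 128) to be deduced in advance. The ceiling assumes knowledge of every earlier allocation and of the block boundaries. With 2 to 4 surgeons who share nothing, the share is about 8% to 2%. The true figure cannot be placed within that range from the protocol.

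It would go too far to say that one third of allocations will be known, or that the VAS comparison is biased. The documents give no estimate of bias and no evidence of selection. What they support is that selection is possible and that a better method is available at almost no cost. The sample size is unaffected.

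**What to change.** Have the independent research administrator generate the list with randomly varying block sizes, for example 4, 6 and 8. Remove the block size from sections 4 and 4.1, state there only that permuted blocks of varying size are used, and keep the sizes in a document that the surgical team cannot see. It would also help for section 4.1 to say who opens the envelope and what happens if a patient is found ineligible at the examination under anaesthesia. This is a clarification and does not carry the point.

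The cost is a change to the list-generation code and to the protocol wording, with no extra patients. With a largest block of 8, stopping mid-block can leave the arms unequal by at most 8 / 2 = 4 patients.

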# **1 BACKGROUND AND RATIONALE**

## **1.1 General Introduction**

Haemorrhoids or piles are the most common colorectal condition in the local population. Patients often present with bleeding with bowel movement or anal discomfort, both of which causes significant anxiety and stress. For symptomatic sizeable piles, the treatment of choice still remains the conventional open excision (COH). However, this technique carries with it a significant risk of bleeding and pain immediately after the operation, leading to some period of discomfort for the patients. The laser haemorrhoidoplasty procedure (LAH) has been shown in preliminary studies to have less pain, and less complications compared to COH. This study aims to directly compare these two techniques in a local Asian population.

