## **2.4 Potential Risks and Benefits:**

### **2.4.1 Potential Risks**

Risk of the participation in the trial include:

- Breach of patient confidentiality and personal data

Risk of General Anaesthesia for both procedures is in keeping with that of those patients not involved in the study. These includes but not limited to:

- Major adverse cardiac events (MACE)
- Cerebral vascular accidents (stroke)
- Barotrauma
- Damage or loss of dentition

Risk of Operation:

a. Conventional open haemorrhoidectomy (COH):

- i. Bleeding
- ii. Anal sphincter injury which may lead to fecal incontinence
- iii. Anal stenosis
- iv. Pelvic sepsis
- v. Recurrence of haemorrhoids

b. Laser haemorrhoidoplasty procedure (LAH):

- i. Bleeding
- ii. Thrombosis
- iii. Anal sphincter injury which may lead to fecal incontinence
- iv. Pelvic sepsis
- v. Bowel injury which may necessitate emergency surgery and/or stoma creation
- vi. Intestinal obstruction which may necessitate stoma creation

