### **2.4.2 Potential Benefits**

The benefits of participation in this trial is that patients will be closely monitored post procedure for their pain and symptoms and will receive a phone calls outside the regular follow up period, up to a year post-procedure, to follow up on their haemorrhoid-related symptoms.

They will also potentially may receive a procedure that could potentially cause less pain and have a lower risk of post-operative bleeding.

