## **9 SAMPLE SIZE AND STATISTICAL METHODS**

### **9.1 Determination of Sample Size**

Based on previous studies, as well as unpublished results from surgeons who have performed LAH around the South East Asian region, we are expecting 50% of the patients in the COH arm to have a VAS score of more than 7.5. We expect to see 25% patients in the LAH arm having a VAS score of more than 7.5.

With a power of 80%, chance of type 1 error (alpha) less than 5% and accounting for 10% of loss to follow up rate, the sample size required for the study to be adequate powered is having 64 patients in each arm (N=128).

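### Concealed allocation and late disclosure are treated as a patient blind, but nothing described keeps the arm hidden on days 0-10, when patients score the primary outcome themselves

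*Protocol*

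**What the plan says.** All references are to the Protocol. Section 4 labels the trial double-blind. Sections 4, 4.1 and 6.5 state that patients are allocated only once they have been examined under anaesthesia, from an opaque envelope brought on the day by a research administrator. Each then draws the same conclusion: "Thus, the patient is blinded to the procedure". Sections 4.3.1 and 6.5 add that the patient learns the allocation at the 4-6 week clinic review.

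The primary objective (2.2) is a daily pain score over the first 10 days, which the patient records in the peri-operative package. Section 4 lists that package's contents. Besides the pain scales for days 0-10, they include particulars of the operation and of the haemorrhoids as found at surgery. Under 4.3.1 the administrators collect the package back from the patient at 4-6 weeks.

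Three further places bear on what patients may expect:
- **Section 4**, on recruiting to a procedure new in Singapore, says that "offering a short video clip of the procedure may be helpful".
- **Section 2.4.2** counts among the benefits of taking part that patients may "receive a procedure that could potentially cause less pain and have a lower risk of post-operative bleeding".
- **Section 2.4.1** has "v. Recurrence of haemorrhoids" in the list for conventional open haemorrhoidectomy (COH). The list for laser haemorrhoidoplasty (LAH) has no such entry.

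**The concern.** Concealing an allocation and maintaining a blind are separate tasks. The first protects the assignment up to the operation. The second has to work afterwards, while the outcome is being recorded. The protocol describes the first and asserts the second.

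This matters because the primary outcome is subjective and self-scored. If some patients know or correctly guess their arm, and expect one procedure to hurt less, part of the observed difference in pain can be expectation rather than treatment effect. A larger sample does not remove such a bias. The trial would also be reported as a double-blind pain comparison on the strength of steps that do not establish it. Section 4 discusses bias in the pain and quality-of-life scores but names only recall and interviewer bias, not expectation.

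**Working it through.** **1. What each step protects.**

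| Step | Section | Before surgery | Days 0-10 |
|---|---|---|---|
| Allocation after examination under anaesthesia | 4, 4.1, 6.5 | Protects | Patient did not witness the allocation; no further effect |
| Opaque envelope | 4, 4.1, 6.5 | Protects | No effect |
| Allocation not disclosed until 4-6 weeks | 4.3.1, 6.5 | n/a | Patient is not told, but may infer |
| Anything that hides which operation was done (dressings, ward staff, records) | None described | n/a | Nothing described |

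The third step does cover the primary window, since 4-6 weeks falls after day 10. What is missing is anything that prevents inference.

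**2. Routes by which the arm could become known.**
- *The operation itself.* Sections 1.1 and 1.2 set an open excision against a laser procedure, and section 12.1 has the risks of the techniques explained to patients. That a patient could recognise which was done is an inference; the protocol does not say so.
- *The package.* Sections 4 and 4.3.1 together place operative details in a package returned by the patient. Section 4 splits the package into pre- and post-operative components, and section 8.2 mentions a separate study-team data sheet. The details may therefore never reach the patient, but no section says that they are withheld.

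**3. Direction of expectation.** Sections 2.1 and 2.4.2 point towards less pain with LAH. Section 2.4.1 gives recurrence for COH only, although recurrence is an outcome in both arms (1.2, 2.3) and section 1.2.1 says that no well-designed randomised trial has yet examined longer-term LAH outcomes. Against this, section 2.4.1 lists thrombosis, bowel injury and intestinal obstruction for LAH only, the last two with possible stoma.

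**4. The plan's own figure.** Section 9.1 states "we are expecting 50% of the patients in the COH arm to have a VAS score of more than 7.5" and 25% for LAH, with 80% power, alpha 5% (two-sided assumed) and 10% loss.

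n per arm = [1.960 × √(2 × 0.375 × 0.625) + 0.8416 × √(0.50 × 0.50 + 0.25 × 0.75)]² / 0.25² = 57.7, so 58.

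58 × 1.1 = 63.8, so 64; or 58 / 0.9 = 64.4, so 65. The stated 64 per arm reproduces and is not in dispute. The planned difference is 50 − 25 = 25 points.

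**5. Illustration of size, on assumed inputs.** Suppose 50-90% of patients correctly infer their arm, and that doing so moves the share scoring above 7.5 by 5-10 points, down in LAH and up in COH.

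Spurious difference = 2 arms × share inferring × shift per arm
- Low: 2 × 0.5 × 5 = 5 points
- High: 2 × 0.9 × 10 = 18 points

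If only one arm shifts, these halve to 2.5 and 9 points. Wrong guesses would reduce them further.

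**6. Effect on the test.** Take no true difference, 58 evaluable patients per arm, rates centred on 50%, and Fisher's exact test (9.2) at two-sided 5%. The chance of a significant result favouring LAH is:

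| Spurious difference | COH vs LAH | Chance |
|---|---|---|
| 0 points | 50% vs 50% | 1.6% |
| 5 points | 52.5% vs 47.5% | 5.4% |
| 10 points | 55% vs 45% | 14.4% |
| 18 points | 59% vs 41% | 42.3% |

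**The case against.** Allocating under anaesthesia and withholding the result until after the pain scores are complete is how a patient blind is ordinarily set up in surgery, and both steps deserve credit. It would be wrong to say that the blind rests on the envelope alone. Participants have also had no previous haemorrhoid operation (3.3, 3.4), so they have no wound of their own to compare with. This stands, but it shows only that the blind may hold. It does not supply a measure that makes it hold.

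A reader might infer more than the protocol supports, in four ways:
- **That it sets out recruitment material slanted towards LAH.** It does not. The clip is only suggested, and its content is not given. Section 2.4 is protocol text and is not shown to be what patients read; its pain claim is hedged.
- **That expectation must run one way.** The serious risks listed for LAH only could make that arm the more worrying one, and section 4 anticipates reluctance about a new procedure.
- **That the 5 to 18 points estimate the bias.** Both inputs are assumed, every inference is taken as correct, and both arms are taken to shift equally.
- **That the trial will certainly have no information on whether the blind held.** The questionnaire package is attached separately and is not shown, so a guess question may already be in it.

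Masking discharge papers might also be suggested. It is not clearly cheap: a patient may present elsewhere with a complication, and section 2.4.1 lists different complications for the two procedures. It is not recommended here.

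**Conclusion.** The point holds as a gap between what the protocol claims and what it provides. The described steps establish concealment and non-disclosure. They do not establish that the patient stays blind on days 0-10, so neither the conclusion drawn in sections 4, 4.1 and 6.5 nor the patient part of the double-blind label is supported as written. The unresolved location of the operative details is a concrete route by which the arm could be revealed.

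Any resulting bias is more likely to favour LAH than COH, given the trial's hypothesis and section 2.4.2. That is a judgement, since the protocol fixes neither size nor direction. The illustration shows only that a spurious difference well below the planned one would matter: at 10 points, the chance of a false finding for LAH would be about nine times its level without bias (14.4 / 1.6). The changes should be made before recruitment, because a guess cannot be collected usefully once the patient has been told the arm.

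**What to change.** 1. **Section 4, recruitment.** If a clip or leaflet is used, give both procedures equal coverage and make no prediction about which hurts less.
2. **Sections 4 and 8.2.** Record operative details only on the study-team data sheet, and state that they do not appear in any component the patient holds.
3. **Section 2.4.** List recurrence for both procedures in 2.4.1. In 2.4.2, say that it is not yet known which procedure causes less pain.
4. **Appendix 2.** Unless the questionnaire already has it, add one day-10 question on which procedure the patient believes was done. Report it by arm beside the primary result, descriptively only, because a guess may itself reflect the pain felt.
5. **Sections 4, 4.1 and 6.5.** State that patients are not told their allocation until the 4-6 week review, in place of the statement that blinding follows from the envelope. Bring the double-blind label into line with this.

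The cost is rewording and at most one extra question in a package that patients already complete, with no added patients or staff. The downside is that a neutral clip may recruit slightly less well.

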## 4.2 Contraception and Pregnancy Testing

For females of childbearing age included in the trial, they will be asked whether they are pregnant and for their last menstrual period. They will be offered a UPT to test for pregnancy during recruitment into the trial but there are no requirements to perform the test.

## 4.3 Study Visits and Procedures

### 4.3.1 Screening Visits and Procedures

Patients will be seen in the clinic or in the wards for symptomatic haemorrhoids. All these patients would be approached and be introduced to this study but not recruited yet.

Figure 2 illustrates the visits commitment throughout the study process. After the completion of surgery, patients typically would already have a follow up appointment at 4-6 weeks after the procedure. The clinician will assess the patients progress and examining them for any complications. If their recovery is smooth, most of these patients would be discharged from follow up. During the same setting, the research administrators would collect back the peri-operative package from the patient.

Research administrators would then conduct a phone interview with the patients at 3-month and 1-year after surgery to perform the QoL survey and also looking out for late-onset complications and recurrence of symptoms. If present, they will be offered to have an appointment booked with their primary surgeon. Patients would be informed of the allocation at the clinic review at 4-6 weeks. As none of the visits are outside of normal practice, no remuneration is required.

